## Introduction

Dental implants have been considered a good option for partially edentulous patients in maintaining healthy mucosa with minimal crestal bone loss and no extensive harm to the adjacent natural teeth (**Henry, P. J, 2000**).

Three basic protocols for implant placement were defined according to the time between tooth extraction and implant installation; in the type-1 protocol (immediate implant installation), implants are placed in fresh extraction sockets, with the aim to engage the remaining socket walls with the implant. In the type-2 protocol (early implant placement), implants are placed approximately 4–8 weeks after tooth extraction. The main objective of this protocol is to ensure the lack of pathology when placing the implant and, at the same time, to optimize the availability of soft tissue for primary healing and probable lateral bone augmentation. In the type-3 protocol (early-delayed/conventional implant placement) the implants are placed once most of the dimensional changes in the alveolar ridge have occurred (12–16 weeks) (**Lanza et al., 2015**).

The early implant-placement protocol has been suggested because it shares some of the advantages of immediate placement, such as using bone volume immediately after extraction, although already in the second month there is alveolar bone loss; it also allows for the primary closure (epithelium-connective tissue) of the wound. It is indicated in the presence of acute infectious processes; early implant placement is associated with a lower frequency of mucosal recession compared to immediate placement, when combined with regeneration procedures (**Sanz et al., 2012**).

Implant therapy in the anterior maxilla is challenging for the clinician because of the esthetic demands of patients and difficult pre-existing anatomy

**(Ebenezer et al., 2015).** Placement of dental implant in the esthetic zone is a technique sensitive procedure with a little room for error **(Al-Sabbagh et al 2006).**

Enough keratinized tissue was considered important for marinating healthy tissue around dental implant, Also soft tissue biotype has been considered as a critical factor, where patients would show either thin scalloped gingiva or thick flat biotype Moreover, it has been proven that thin biotype had higher liability for gingival recession from any trauma during the surgical and prosthetic procedures in comparison to thick flat biotype and the underlying bone could suffer from rapid resorption in association with soft tissue recession **(Elbattawy et al.,2020).**

Consequently, plastic augmentation procedures have been introduced to achieve better esthetics in conjunction with implant placement **(Burkhardt & Lang 2014).** There is consensus that the addition of soft tissue graft to the surgical implant protocol in patients with thin scalloped biotype increases gingival thickness and improves esthetic outcomes, especially at the buccal gingival margin level. It is likely to even improve longer-term soft tissue stability **(Shetty & Bhat 2013).**

Subepithelial Connective Tissue Graft has been widely utilized aiming at increasing the width and thickness of keratinized tissue either around natural teeth or around implants for resisting and treating recession, masking the metallic implant color and also for papillary reconstruction **(Karthikeyan et al., 2016).** Both free gingival and connective tissue grafts are however associated with significant patient morbidity due to the need for a donor palate site, that leaves the periosteum exposed after surgery. Unfortunately, high morbidity is common in all types of surgeries where autologous grafts are

involved (like bone grafting techniques), while xenogeneic materials do not present such inconvenience (**Puri et al., 2019**).

An ideal non autologous graft for soft tissue substitution should promote haemostasis, be infection resistant, favour the formation of granulation tissue, have a low post-operative morbidity and have a fast healing time (**Maiorana et al., 2016**).

Mucoderm® is a natural type I/III collagen matrix derived from porcine dermis that undergoes a multi-stage purification process to remove all non-collagenous proteins and cells, as well as potential bacteria and viruses. These processing results in a three-dimensional stable matrix consisting of a naturally cross-linked open porous collagen network that serves as a scaffold for the adhesion and migration of connective tissue cells and blood vessels (**Pabst et al. 2015**). Thus, mucoderm® supports revascularization, fast soft tissue integration and offers a safe alternative to the autologous connective tissue (**Schmitt et al. 2016, Zafiropoulos et al. 2016, Rossi et al. 2016**).

Mucoderm will be used in this study as axenogenic collagen matrix for soft tissue augmentation in maxillary esthetic zone

### **Aim of the study**

The aim of this study is to compare the clinical and radiographic outcomes of xenogeneic collagen matrix to Subepithelial Connective Tissue Graft in maintaining crestal bone and enhancing soft tissue around early implant placement in maxillary anterior zone

## **Patients and methods**

### **Patient selection**

This investigation will be included 12 implants placed in 12 patients with missing maxillary tooth in the esthetic zone. Subjects will be selected from the outpatient clinic, Department of oral Medicine and Periodontology, Faculty of Dentistry, Minia University.

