### **Ethical regulation**

The complete treatment plan will be explained to all patients including detailed steps, risks, and expected results and their full signed consent will be obtained prior to entry into study. The study will be complied with the rules

set by the International Conference on Harmonization Good Clinical Practice Guidelines, and the Declaration of Helsinki and the research ethics committee of the Faculty of Dentistry, Minia University.

Clinical evaluation:

Patients will be evaluated clinically and radiographically along the course of the study at baseline, 6, 12 months after the implant insertion.

The following records will be performed:

1-Clinical photographs, Study casts at baseline.

2-A preoperative cone beam computed tomography (CBCT) will be performed for each patient prior to the surgery to determine bone height and width and decide the implant length and diameter to be placed and to evaluate the underlying bone condition.

3-Full mouth periodontal parameters will be recorded using William% graduated periodontal probe to evaluate the periodontal status (plaque index, gingival index, pocket depth, clinical attachment loss).

4-Trans-gingival probing will be done at the mesial line angle 2, 4 and 6 mm apical to the gingival margin. At the same apico-coronal direction three points will be recorded at the mid-buccal and at the distal line angle (**Rotenberg & Tatakis, 2014**).

5-The width of keratinized gingiva will be measured using graduated periodontal probe and recorded as the distance from the mucogingival junction to the gingival margin

Assessment methods:

Patients will be evaluated clinically and radiographically along the course of the study (immediate after the implant insertion) at baseline 0, 6 and 12 months.

Clinical assessment:

Clinical parameters will be included: gingival thickness (GT), keratinized tissue width (KTW)

GT will be measured by trans gingival-piercing of the tissues using an anesthetic needle with a rubber stopper 2mm coronal to the MGJ and in the mid distance mesio-distally. KTW will be measured at the mid buccal area from the gingival crest to the MGJ

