### **Randomization**

The study will be used simple randomization to allocate patients into test and control groups.

Then, random allocation will be performed using computer-generated random numbers to determine which group they will be assigned

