**Radiographic assessment:**

-Radiographic evaluation will be performed for all patients at baseline, 6 and 12 months following treatment by using cone beam CT

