Soft Tissue Augmentation by Xenogeneic Collagen Matrix Versus Subepithelial Connective Tissue Gra

Statistical Analysis Plan

Document Type: Statistical Analysis Plan

NCT Number: (To be assigned)

Document Date: July 3, 2021

Submitted by:

[name]

PhD Candidate

Faculty of Dentistry

Minia University

1. Study Identification

- Protocol ID: 505/2021
- Sponsor: Minia University
- Investigator: [name] [name] Candidate

2. Study Objectives

- To compare the clinical outcomes of xenogeneic collagen matrix (XCM) and subepithelial connective

3. Endpoints

- Primary Endpoint: Change in peri-implant soft tissue thickness at 12 months (in mm).

4. Study Design Summary

- Randomized controlled trial with two parallel arms.
- 20 patients (10 per group), assigned to either SCTG or XCM group.
- Outcome assessed by a blinded evaluator.

5. Sample Size Justification

- Based on clinical experience and prior literature, a sample size of 10 per group was determined to

6. Statistical Methods

- Descriptive statistics (mean, SD) will be used for baseline characteristics.
- Independent Samples T-test will be used to compare changes in soft tissue thickness between groups.
- Significance level set at $p < 0.05$.
- Confidence interval: 95%

7. Missing Data Handling

- Missing values will be managed using pairwise deletion. No imputation methods are planned.

8. Software to be Used

- Statistical analysis will be conducted using SPSS version 25 (IBM Corp.).

9. Data Presentation

- Data will be presented in tables (means \pm SD).
- Results will be illustrated using bar charts to compare primary outcomes.

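### The protocol plans 12 patients in total and the SAP plans 20 (10 per group), and no text available for review reconciles the two or says which governs

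*Protocol*

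**What the plan says.** The protocol gives its only sample size under Patient selection: "This investigation will be included 12 implants placed in 12 patients with missing maxillary tooth in the esthetic zone". It states no number per group, no calculation and no allowance for dropout. Its Statistical analysis section is a single general sentence.

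The SAP states in section 4: "20 patients (10 per group), assigned to either SCTG or XCM group". Section 5 repeats the group size: "Based on clinical experience and prior literature, a sample size of 10 per group was determined to". That sentence breaks off in the text available for review, and nothing is inferred here about how it ends.

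The SAP carries a date: "Document Date: July 3, 2021". The protocol text available for review carries none, but its title pages are not part of that text. On missing data, SAP section 7 says: "Missing values will be managed using pairwise deletion. No imputation methods are planned".

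**The concern.** The two documents describe the same two-arm trial with different totals. The total determines when enrolment is complete and how precisely the primary endpoint can be compared between groups. While both numbers stand, a trial that stops at 12 and one that stops at 20 can each claim to have followed its plan. A reader of the results could not tell a completed trial from one that stopped 40% short, or a planned 12 from an overrun to 20.

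One figure may simply be outdated rather than mistaken. That would explain the difference, but nothing available for review says so or shows which figure came first.

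**Working it through.** **Inputs.**
- Protocol total: 12 patients with 12 implants (Patient selection).
- SAP total: 20 patients, 10 per group (sections 4 and 5).
- Primary endpoint: change in peri-implant soft tissue thickness at 12 months, in mm (SAP section 3).
- Test: independent-samples t-test at the 5% level, with 95% confidence intervals (SAP section 6).
- Assumed: two-sided test, equal arms, common SD.
- Not given in the text available for review: SD, effect size, power, dropout rate. All results are therefore in units of the SD of the change.

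**Can either total be reproduced?** The SAP is consistent with itself: 2 × 10 = 20. Neither 12 nor 20 can be derived from an effect size and power, because none is given.

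**Can the totals be linked?**
- *Implants versus patients.* The protocol equates 12 implants with 12 patients, so multiple implants per patient cannot explain the gap.
- *12 per arm.* This gives 2 × 12 = 24, not 20, and the protocol sentence describes the whole investigation.
- *20 enrolled, 12 evaluable.* This needs attrition of 1 − 12/20 = 40%, and no text available for review allows for any attrition.

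The gap is 20 − 12 = 8 patients: 20 is 67% more than 12, and 12 is 40% fewer than 20.

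**Precision.** Half-width of the 95% confidence interval = t(0.975, N − 2) × √(1/n₁ + 1/n₂).
- 6/6: 2.228 × √(2/6) = 1.286 SD
- 10/10: 2.101 × √(2/10) = 0.940 SD
- Ratio: 1.286 / 0.940 = 1.37, so the interval is 37% wider at 12 patients.

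**Power.** Noncentral t with N − 2 degrees of freedom and noncentrality δ√(n/2), where δ is the true difference in SD units and n the number per arm.

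| | 12 patients (6/6) | 20 patients (10/10) |
|---|---|---|
| Difference detectable with 80% power | 1.80 SD | 1.32 SD |
| Power at 0.8 SD | 24% | 39% |
| Power at 1.0 SD | 35% | 56% |
| Power at 1.2 SD | 47% | 72% |
| Power at 1.32 SD | 54% | 80% |
| Power at 1.5 SD | 65% | 89% |

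**Losses.** Without imputation, each patient lacking the 12-month value drops out of the primary comparison. With one loss per arm (illustrative), the half-widths are 2.306 × √(2/5) = 1.458 SD at 5/5 and 2.120 × √(2/9) = 0.999 SD at 9/9, a ratio of 1.46.

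**The case against.** The strongest reply is that the record is incomplete. The protocol's title pages are not in the text available for review and the SAP's sample size sentence is cut off, so a protocol date, a version number or a statement of precedence may exist there. This stands as a limit on the claim: it cannot be said that no such statement exists anywhere. It does not remove the conflict, because both totals are complete sentences in the available text. Missing text could explain the difference but could not make 12 equal 20.

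A second reply is that the power figures do not show either total to be inadequate. This is also right. The 1.32 SD difference was chosen because it gives 80% power at 20 patients. It shows what separates the two totals, not what difference should be expected.

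A third is that the one-loss-per-arm comparison overstates the gap, because one loss is 17% of six patients but 10% of ten. At similar loss rates, 5/5 against 8/8 (17% and 20%), the half-widths are 1.458 and 2.145 × √(2/8) = 1.072 SD, a ratio of 1.36. That is essentially the no-loss ratio, so 37% is the figure to use.

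**Conclusion.** The concern holds. The planned sample size is stated as 12 in one document and 20 in the other, and the readings that might join them all fail. Which total is correct cannot be determined from these documents.

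The choice changes the expected half-width for the primary comparison from 0.94 to 1.29 SD and the difference detectable with 80% power from 1.32 to 1.80 SD. Those figures rest on equal arms, a two-sided 5% pooled t-test and no losses. The contradiction itself rests on none of these assumptions. It must be corrected, because a core design parameter is wrong in at least one document.

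**What to change.** State one operative total in both documents, and add a dated note saying which number was planned first and why the other differs.

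- **If 12 is operative:** change SAP section 4 to 12 patients. Rewrite section 5, whose rationale is given for 10 per group, so that it supports the smaller number, and state the resulting precision (half-width about 1.29 SD at 6/6). The cost is text and a new rationale. The lower precision would be a consequence of the design, not of the correction.
- **If 20 is operative:** change the Patient selection sentence to 20 implants in 20 patients, with whatever amendment is required by "the research ethics committee of the Faculty of Dentistry, Minia University". If recruitment was planned at 12, this also means 8 more patients, each followed for 12 months. The protocol's imaging plan reads: "Radiographic evaluation will be performed for all patients at baseline, 6 and 12 months following treatment by using cone beam CT". That is 8 × 3 = 24 further scans, or 8 × 4 = 32 if the preoperative scan is separate. The protocol's Assessment methods text places baseline immediately after implant insertion, which favours 32.

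A smaller drafting point applies in either case. The Randomization section says: "The study will be used simple randomization to allocate patients into test and control groups". Simple randomization does not guarantee a fixed group size. At an assumed 1:1 ratio, the chance of an exact split is C(20,10)/2²⁰ = 17.6% for 10/10 and C(12,6)/2¹² = 22.6% for 6/6. Group sizes are better given as approximate unless the allocation method changes.

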#### **Inclusion criteria:**

- 1-Selected patients of both sexes are 25-55 years old.
- 2-Patient will be free from any systemic diseases that might affect healing, or complicate the surgical procedures according to modified Cornell Medical Index(**Glick M.,2003**)
- 3- Thin tissue biotype ,Trans-gingival periodontal examination will be made 2, 4 and 6 mm apical to the gingival margin at the mesiolabial and distolabial line angle as well as midlabial (**Cuny-Houchmand et al., 2013**)
- 4- Cooperative, motivated, and hygiene conscious patients.

#### **Exclusion criteria:**

- 1- Pregnant women.
- 2-Smokers
- 3-Precense of persistent chronic infection in the implant site.
- 4- Patient at growth phase with partially erupted teeth
- 5- Patient with para-functional habits that produce overload on the implant such as bruxism and clenching
- 6- Patient with insufficient vertical inter-arch space upon centric occlusion to accommodate the available restorative component

### **Ethical regulation**

The complete treatment plan will be explained to all patients including detailed steps, risks, and expected results and their full signed consent will be obtained prior to entry into study. The study will be complied with the rules

set by the International Conference on Harmonization Good Clinical Practice Guidelines, and the Declaration of Helsinki and the research ethics committee of the Faculty of Dentistry, Minia University.

Clinical evaluation:

Patients will be evaluated clinically and radiographically along the course of the study at baseline, 6, 12 months after the implant insertion.

The following records will be performed:

1-Clinical photographs, Study casts at baseline.

2-A preoperative cone beam computed tomography (CBCT) will be performed for each patient prior to the surgery to determine bone height and width and decide the implant length and diameter to be placed and to evaluate the underlying bone condition.

3-Full mouth periodontal parameters will be recorded using William% graduated periodontal probe to evaluate the periodontal status (plaque index, gingival index, pocket depth, clinical attachment loss).

4-Trans-gingival probing will be done at the mesial line angle 2, 4 and 6 mm apical to the gingival margin. At the same apico-coronal direction three points will be recorded at the mid-buccal and at the distal line angle (**Rotenberg & Tatakis, 2014**).

5-The width of keratinized gingiva will be measured using graduated periodontal probe and recorded as the distance from the mucogingival junction to the gingival margin

Assessment methods:

Patients will be evaluated clinically and radiographically along the course of the study (immediate after the implant insertion) at baseline 0, 6 and 12 months.

Clinical assessment:

Clinical parameters will be included: gingival thickness (GT), keratinized tissue width (KTW)

GT will be measured by trans gingival-piercing of the tissues using an anesthetic needle with a rubber stopper 2mm coronal to the MGJ and in the mid distance mesio-distally. KTW will be measured at the mid buccal area from the gingival crest to the MGJ

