### **Treatment plan:**

All procedures will be done under completely aseptic conditions.

Patients will be anaesthetized by buccal and palatal infiltration.

Crestal incision and full thickness mucoperiosteal flap will be elevated buccally and lingually. Then the bone width will be measured again using bone caliper to confirm the implant width as detected in CBCT.

Sequential drilling will be started by the pilot drill till the last drill that suited the planned implant size. Before implant placement a parallel pin will be used to check the implant parallelism.

Implant insertion will be done in the osteotomy site using torque wrench by self-tapping fashion till the implant will be placed 0.5-1mm below the alveolar bone crest with adequate primary stability

The site will be prepared to receive the graft and allow its fixation.

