#### **Group1 (control group):**

SCTG will be from the palate by single incision technique .The SCTG will be placed in the pouch over the recipient site below the labial/buccal flap and extending palatally. The graft will be sutured in a horizontal mattress manner to the labial/buccal flap .The palatal wound from which the SCTG harvested, will be sutured by sterilized, natural non absorbable silk

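### The primary endpoint does not say what its 12-month change is measured from, and the only timing the protocol attaches to baseline falls within the grafting operation

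*Protocol*

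**What the plan says.** SAP section 3 gives "Primary Endpoint: Change in peri-implant soft tissue thickness at 12 months (in mm" and stops there. SAP section 6 adds "Independent Samples T-test will be used to compare changes in soft tissue thickness between groups", again with no starting point. The SAP does not expressly tie the endpoint to the protocol's gingival thickness (GT) measure, although GT is the likely match.

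The protocol has two clinical schedules, both in the text under Ethical regulation. Under Clinical evaluation: "Patients will be evaluated clinically and radiographically along the course of the study at baseline, 6, 12 months after the implant insertion". Under Assessment methods, directly above the methods for GT and keratinized tissue width (KTW), patients are evaluated clinically and radiographically "along the course of the study (immediate after the implant insertion) at baseline 0, 6 and 12 months".

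GT is then read "using an anesthetic needle with a rubber stopper 2mm coronal to the MGJ and in the mid distance mesio-distally", MGJ being the mucogingival junction. The list of records has a different thickness measurement: "Trans-gingival probing will be done at the mesial line angle 2, 4 and 6 mm apical to the gingival margin", with matching points mid-buccally and at the distal line angle. Item 5 of that list is keratinized width. Neither item is dated.

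The Treatment plan runs from flap elevation through implant insertion to "The site will be prepared to receive the graft and allow its fixation". For the control arm, "The SCTG will be placed in the pouch over the recipient site below the labial/buccal flap and extending palatally".

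**The concern.** A change score is defined only when both of its time points are defined. Here the 12-month end is fixed and the starting end is not. An examiner who follows the assessment section literally would take the starting value during the operation that delivers the randomised treatment. If that value is taken after the graft is fixed, it already contains the graft. The stated aim is to compare the two materials in enhancing soft tissue; a change from such a baseline would instead describe how much of each graft is lost. The same 12-month tissue could be reported as a gain or as a loss depending on when one needle reading is made. A pre-incision reading that was not taken cannot be recovered later.

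**Working it through.** No figure in the plan bears on baseline timing, and the visible SAP text gives no SD or effect size, so there is nothing to reproduce. The check is a reading of the text followed by an identity.

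**Step 1: which times are stated**

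| Place | Timing given for the starting value |
|---|---|
| SAP sections 3 and 6 | None |
| Protocol, Clinical evaluation schedule | Baseline, undated; months count from insertion |
| Protocol, Assessment methods | Directly after implant insertion |
| Protocol, Radiographic assessment | Baseline, undated |
| Protocol, records item 2 | Preoperative, but this is the planning CBCT for bone |
| Protocol, records items 4 and 5 | Undated |
| Protocol, inclusion criterion 3 | Before treatment by implication; an eligibility examination |

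The thickness probing in inclusion criterion 3 and in records item 4 is located 2, 4 and 6 mm from the gingival margin. GT is located 2 mm from the MGJ. The documents do not make these the same point, so the probing values cannot simply be subtracted from a 12-month GT.

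**Step 2: where insertion falls.** The Treatment plan and Group 1 text place graft preparation and fixation after insertion, and no separate grafting session is described. That insertion and grafting are one operation is an inference, but the natural one. Three baselines are then possible: before incision, between insertion and grafting, or after graft fixation. For the middle one, nothing in the documents describes such a reading and no between-arm bias is shown, so nothing is claimed for it.

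**Step 3: the identity.** Let T0 be native thickness, G the thickness added as placed, and T12 the 12-month thickness.

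- Change from pre-incision: T12 − T0 (net gain).
- Change from post-graft: T12 − (T0 + G) = net gain − G.
- With D the between-arm difference in mean G: post-graft contrast = net-gain contrast − D.

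This needs no SD and no distribution. If D = 0 the two contrasts are equal, even when the materials differ in retention.

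**Step 4: illustration with equal retention.** All values are assumed, because the documents give no graft thickness or retention. If both arms retain the same share r of the added thickness and all else is equal, the net-gain contrast is rD and the post-graft contrast is −(1 − r)D. Each cell shows net-gain / post-graft contrast in mm, thicker-graft arm minus the other:

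| D | r = 0 | r = 0.5 | r = 0.7 | r = 1 |
|---|---|---|---|---|
| 0.25 | 0 / −0.25 | +0.125 / −0.125 | +0.175 / −0.075 | +0.25 / 0 |
| 0.5 | 0 / −0.5 | +0.25 / −0.25 | +0.35 / −0.15 | +0.5 / 0 |

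For r strictly between 0 and 1 the signs are opposite.

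**Step 5: illustration with unequal retention.** Suppose arm A adds 1.5 mm and keeps 90%, and arm B adds 1.0 mm and keeps 70%.

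- Net gains: 1.5 × 0.9 = 1.35 and 1.0 × 0.7 = 0.70; contrast +0.65.
- Changes from post-graft: 1.35 − 1.5 = −0.15 and 0.70 − 1.0 = −0.30; contrast +0.15.
- Identity: 0.65 − 0.5 = 0.15, as required.

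The contrast shrinks but keeps its sign. Within arm B alone, the same tissue reads +0.70 mm from pre-incision and −0.30 mm from post-graft.

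**The case against.** The best defence is that baseline is meant to be pre-operative. The parenthesis about insertion is awkwardly placed and may only restate the origin of the month count, as the Clinical evaluation schedule does. The sentence also covers imaging, for which a post-insertion reference is natural. Thin biotype must be established before treatment, and records items 4 and 5 are listed beside baseline photographs, casts and the preoperative CBCT. This may well be the intention, and if so only wording is at fault. It does not settle the matter, because the sentence also covers clinical evaluation and stands directly above the GT method, and no pre-operative reading at the GT point is specified.

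Two stronger readings are tempting and should be resisted:

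- A reader might infer that the trial takes its baseline after the graft is fixed. Neither document says so; the parenthesis names insertion, not fixation.
- A reader might infer that the primary comparison is biased or will point the wrong way. That requires a post-graft baseline and unequal as-placed thickness, and reversal also depends on retention, as Step 5 shows. The arms receive autologous tissue and a collagen matrix, so equal retention should not be presumed.

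Rejection rates add little here. With an assumed SD of change of 0.5 mm, D = 0.5 and r = 0.7, the post-graft t-test (two-sided 0.05) would be significant in about 10% of trials with the SAP's 10 per arm. With 6 per arm (the protocol's 12 patients split equally) the figure is 8%. The point rests on the identity, not on these figures.

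**Conclusion.** The concern holds as a gap in the definition of the only listed primary endpoint. The change has no stated reference time, and the one timing given for baseline lies within the grafting operation without saying on which side of graft fixation. It should be fixed.

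The consequence is conditional. It arises only if baseline is read after fixation and the graft covers the GT point; cover is likely, but the Group 1 text does not say how far apically the graft extends. The between-arm contrast then shifts by exactly the difference in as-placed thickness, which neither document states or equalises. With equal thickness there is no between-arm bias, although each arm's own gain could still appear as a loss. Size and direction cannot be derived from the documents. Confidence is medium, because the intention may be a pre-operative baseline.

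**What to change.** - State in both the protocol and the SAP that the primary endpoint is GT at 12 months minus GT read before incision, with the same needle method at the same point (2 mm coronal to the MGJ, midway mesio-distally).
- Take baseline KTW before incision too, and say so; records item 5 may already supply it.
- Make the two clinical schedules agree, and give the soft-tissue baseline separately from the radiographic one.
- If GT is also read immediately after grafting, report it separately as a measure of graft remodelling.

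The cost is wording in two documents and fixing one needle reading and the KTW measurement before the incision. No extra visit or patient is needed.
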